APPENDIX C – ADDITIONAL MRI DERIVATION DETAIL

AMRA MRI data, derivations, and analysis rules for REACH Study 1821-FSH-301:

MRI DATA FOR INDIVIDUAL MUSCLES:

MRI tests will be performed at Screening, Week 24, and Week 48 and a total of 36 individual muscles from 4 main body regions (i.e., neck, arm, torso, and leg) will be assessed (See **Attachment A**). Eighteen (18) muscles come from the Left side of the body and 18 come from the Right side. For the MRI analysis, results from Left and Right muscles will be designated as Dominant and Non-Dominant muscles in accordance with the patient's reported arm dominance (as collected on the CRF).

For each individual muscle, trained anatomical imaging experts from the Vendor (AMRA) will calculate the muscle tissue measurements (Lean Muscle Volume [LMV], Muscle Fat Fraction [MFF], and Muscle Fat Infiltration [MFI]), assign a muscle category code (A, B, or C), and evaluate the MRI signal quality for any potential issues that may affect the results. Individual muscle category and MRI signal quality will be used to determine eligibility of a muscle for the MRI analysis.

AMRA derives these results for each individual muscle and provides this set of 3 muscle tissue measurements plus 3 Statistical Inclusion (SI) variables:

- **LMV** is a measure of the lean ('fat-free') muscle tissue volume. Results are reported in liters (L).
- **MFF** is a measure of the overall fattiness of the muscle. MFF results are reported as percentages ranging from 0% (representing no fat) to 100% (representing a completely fat-replaced muscles).
- **MFI** is the fat fraction in the leaner ('fat-free') parts of the muscle and is a proxy for the quality of the portion of the muscle that may still retain a relevant amount of functionality. MFI results are reported as percentages with expected values ranging from 0% to 50%.
- **SI Category (SI_{cat})**: A, B, C muscle category codes are assigned based on MFF and MFI:

MFF Criteria		MFI criteria	Muscle Category	SI _{cat}
MFF < 50%	and	MFI < 10%	Normal	A
MFF < 50%	and	MFI ≥ 10%	Affected	B
MFF ≥ 50%	-	-	End-stage	C

where:

- A. Normal = a muscle that appears normal and is most likely not affected by disease.
- B. Affected = a muscle that is more likely to have disease involvement.
- C. End-stage = a muscle that is most likely to have loss of functional capacity.
- **SI Cross-sectional Quality Flag (SI_{cross})**: with values of 0 or 1 (where 0 = presence of a **major** signal quality issue indicating an unreliable measurement; and 1 = signal quality is otherwise acceptable

REACH TRIAL

for the Cross-sectional analysis). If $SI_{cross} = 0$, the muscle will not be included in the Cross-sectional analysis.

- **SI Longitudinal Quality Flag (SI_{long}):** with values of 0 or 1 (where 0 = presence of **major or minor** signal quality issues; and 1 = signal quality is otherwise acceptable for the Longitudinal analysis). If $SI_{long} = 0$, the muscle will not be included in the Longitudinal analysis.

Planned REACH Study Objectives for Individual MRI Results (Exploratory)

In accordance with the Protocol schedule of assessments, AMRA will provide the set of derived results for each individual muscle per subject per MRI performed at Screening, Week 24, and Week 48. Fulcrum will use the individual muscle results from AMRA to support exploratory objectives:

- Change from baseline in MRI Individual Muscle Measures (MFI, MFF, LMV) at Week 48.

MRI DATA FROM COMBINED MUSCLE GROUPS:

In addition to providing the individual muscle MRI measures and signal quality flags, AMRA also provides a comprehensive set of highly derived composite results from multiple sets of combined muscle groups. AMRA calculates composite MRI results for 2 purposes:

1. Cross-sectional analysis (to evaluate status of disease at a specific point in time).
2. Longitudinal analysis (to evaluate progression of disease over time).

MRI CROSS-SECTIONAL ANALYSIS DATA

For cross-sectional analysis, AMRA calculates composite results from groups of individual muscles in body regions that are associated with a particular functional test. For example, cross-sectional composite results from Dominant Neck + Arm + Torso MRI muscle groups may be used for analysis of correlation with RWS functional test results in the Dominant Arm.

AMRA provides the derived cross-sectional results as a set of 3 total composite measurements:

- **LMV_{tot}:** total cross-sectional composite LMV = calculated sum of LMV values from all eligible muscles ($SI_{cross} = 1$) in the specified cross-sectional body region. LMV_{tot} values are reported in L.
- **MFI_{tot}:** total cross-sectional composite MFI = calculated ratio (proportion) based on the sum of all LMV-adjusted MFI values from all eligible muscles ($SI_{cross} = 1$) in the cross-sectional body region. MFI_{tot} ratio values are then converted and reported as percentages.
- **MFF_{tot}:** total cross-sectional composite MFF = calculated ratio (proportion) based on the difference between 1 (indicating all fat-replaced) and the proportion of lean-to-total muscle volume (LMV_{tot} / TMV_{tot}), where LMV_{tot} is the sum of LMV values and TMV_{tot} is the sum of TMV values from all eligible muscles ($SI_{cross} = 1$) in the cross-sectional body region. MFF_{tot} ratio values are also converted and reported as percentages.

REACH TRIAL

These are the equations AMRA uses to derive these cross-sectional composites:

[figure not shown]
$$LMV_{tot} = \sum_{i \in muscles} SI_{cross,i} \cdot LMV_i$$

$$MFI_{tot} = \frac{\sum_{i \in muscles} SI_{cross,i} \cdot MFI_i \cdot LMV_i}{\sum_{i \in muscles} SI_{cross,i} \cdot LMV_i}$$

$$MFF_{tot} = 1 - \frac{\sum_{i \in muscles} SI_{cross,i} \cdot LMV_i}{\sum_{i \in muscles} SI_{cross,i} \cdot TMV_i}$$

Note: AMRA does not directly provide TMV values for each individual muscle in the data transfer. However, TMV (L) may be calculated from the LMV (L) and MFF (ratio) values using the formula:

$$TMV = LMV / (1-MFF)$$

MRI LONGITUDINAL ANALYSIS DATA

Longitudinal analysis uses AMRA-derived MRI results from whole-body groups of muscles that are defined using SI_{cat} (muscle category) and SI_{long} (longitudinal signal quality flag) values as follows:

- **B Muscles:** all individual muscles with $SI_{cat} = B$ and $SI_{long} = 1$ at Screening (Baseline).
- **A Muscles:** all individual muscles with $SI_{cat} = A$ and $SI_{long} = 1$ at Screening (Baseline).
- **A+B Muscles:** all individual muscles with $SI_{cat} = (A \text{ or } B)$ and $SI_{long} = 1$ at Screening (Baseline).

Important Note: once an individual muscle is assigned to a particular Longitudinal Analysis Muscle Group at Screening (Baseline), the muscle will continue to be followed as such throughout the study. For example, muscles assigned to the **B Muscles** group at Screening (Baseline) will continue to be included in the **B Muscles** group at subsequent visits, regardless of any Post-baseline change in muscle category (e.g., even if a Post-baseline SI_{cat} shifts from B to either A or C, the muscle will still be included in the **B Muscles** group). However, if signal quality at a subsequent visit is deemed unacceptable for Longitudinal analysis (i.e., if Post-baseline SI_{long} shifts from 1 to 0), results from that muscle will not be included in the Longitudinal composite results for that muscle group at that Post-baseline visit (but may still be eligible to be included again at a later visit, if signal quality issues resolve and SI_{long} shifts back from 0 to 1).

Longitudinal Composites: Derived Results From AMRA

For each separate Longitudinal Muscle Group (e.g., B Muscles, A Muscles, A+B Muscles), AMRA provides a set of highly derived longitudinal composite measurements from all eligible muscles at Screening, Week 24, and Week 48 as follows:

- **At Screening:** AMRA provides a derived set of initial study-level **Reference Screening** values at the Screening Visit, based on the number of muscles eligible for longitudinal analysis ($SI_{long} = 1$), and reports these longitudinal composite results as LMV_{tot} (unit = L), MFF_{tot} (unit = %), and MFI_{tot} (unit = %). In addition, AMRA provides a total LMV muscle count (n) of the number of eligible muscles with a non-missing LMV value at the Screening visit.
- **At Week 24:** AMRA provides a derived set of visit-level **Change from Reference Screening** results. These visit-level results comprise an overall count of muscles that are still eligible for analysis at Week 24, plus 4 visit-level Reference Screening values, and 4 visit-level Change from Reference Screening values as follows:
 - (Step 1) AMRA calculates the Week 24 **Reference Screening** values based on the set of muscles that are still eligible ($SI_{long} = 1$). (Note: if new signal quality issues are identified, the eligible muscle count will change and the Reference Screening values will be updated; otherwise, if the muscle count has not changed, the Reference Screening values at Week 24 remain the same as the initial study-level Reference Screening values at Screening). AMRA also refers to these as **Reference Timepoint 1 (TP1)** values and provides them as a set of 4 results: Reference Screening LMV muscle count, LMV_{tot} , MFI_{tot} , and MFF_{tot} .

- (Step 2) AMRA calculates the **Week 24** actual values based on the same set of muscles eligible at this visit. AMRA also refers to these as **Timepoint 2 (TP2)** values. Note: these TP2 results are interim values that AMRA uses for the calculations but does not directly provide them in the MRI data transfer to Fulcrum (see additional details below in the Section for Post-Data Transfer Processing Steps).
- (Step 3) AMRA derives the **Week 24 Change from Reference Screening** values using the Week 24 TP1 and TP2 values (from Steps 1 and 2 above). AMRA provides these change results in the data transfer as a set of 4 highly derived longitudinal composite results:
 - absolute change in LMV_{tot} (unit = L),
 - relative change in LMV_{tot} (unit = %),
 - absolute change in MFF_{tot} (unit = percentage points),
 - absolute change in MFI_{tot} (unit = percentage points).
- **At Week 48:** AMRA repeats the process (as noted above for Week 24) and provides a similar set of visit-level **Reference Screening** and **Change from Reference Screening** at Week 48 values in the data transfer to Fulcrum. Note: for the Week 48 visit, AMRA also includes an extra set of composites that are calculated using Week 24 as the Reference TP1 instead of Screening. However, for the double-blind placebo-controlled portion of the study, this extra set of Reference Week 24-as-TP1 results will not be used; only Reference Screening TP1-based results will be used for this portion of the study.

Longitudinal Composites: Post-Data Transfer Processing Steps

Once AMRA provides the highly derived longitudinal composite results, Fulcrum will perform some additional post-data transfer processing steps to prepare the longitudinal results for analysis.

Calculate Actual TP2 Analysis Values

Since AMRA does not directly provide the actual TP2 values, these analysis values will be calculated in accordance with a rule provided by AMRA, which is a standard sum of the visit-level values:

$$TP2 = (\text{Reference TP1} + \text{Absolute Change from Reference TP1})$$

Apply LMV-based Inclusion Criteria

AMRA provides instructions for Fulcrum to use on each set of visit-level composite values to determine the overall final eligibility of the results for the Longitudinal analysis. AMRA has determined that the reliability of results from a longitudinal analysis requires an adequate level of LMV_{tot} from a sufficient number of muscles. Consequently, if longitudinal LMV_{tot} is below a certain threshold value and the

REACH TRIAL

LMV muscle count is too low, AMRA recommends that the entire set of longitudinal results from that visit should be reset to missing and should not be included in the longitudinal analysis.

So, for each set of visit-level longitudinal results, Fulcrum will check the AMRA derived data and ensure that at least 1 of the 2 following inclusion criteria are met (as instructed by AMRA):

To be included, the Reference Screening (TP1) LMV_{tot} and LMV muscle count must be either:

- at least 25 cl (0.25 L) with measurements from at least 2 muscles, **or**
- at least 50 cl (0.50 L) with measurement(s) from at least 1 muscle.

If the Reference Screening TP1 values do not meet at least 1 of the 2 LMV-based criteria, the entire set of results for all 3 composite measures (LMV_{tot} , MFI_{tot} , and MFF_{tot}) at that visit will be reset to missing and excluded from the longitudinal analysis. Fulcrum will apply these post-data transfer steps to the AMRA data at all visits (Screening, Week 24, and Week 48).

Planned REACH Study Objectives for MRI Longitudinal Results (Secondary and Exploratory)

Per the Protocol schedule, AMRA will provide longitudinal MRI composite results at Screening, Week 24, and Week 48. Fulcrum will use the longitudinal results from AMRA to support 1 planned secondary objective and several planned exploratory objectives.

Longitudinal MRI Secondary Efficacy Endpoint:

- Change from baseline in WB MRI Longitudinal Composite MFI (MFI_{tot}) in B Muscles at Week 48.

AMRA calculates and provides the longitudinal composite results for this secondary endpoint. Fulcrum applies the LMV-based inclusion criteria rules (as instructed by AMRA) and determines the final set of evaluable longitudinal results.

AMRA first identifies the longitudinal analysis set of **B Muscles** (i.e., muscles with $SI_{cat} = B$ at Baseline with $SI_{long} = 1$) and derives the composite measurements at each visit.

Absolute Change from Baseline in MFI_{tot} in B Muscles at Week 48 is described here using AMRA terminology and equations:

- Baseline MFI_{tot} = AMRA-derived Reference Screening TP1 value for MFI_{tot} at Week 48 (unit: %).
- Absolute Change from Baseline MFI_{tot} at Week 48 = AMRA-derived MFI_{tot} Change from Reference Screening at Week 48 value (unit: percentage points).

[figure not shown]
The equation AMRA uses to calculate absolute change in MFI_{tot} at Week 48 for B Muscles is:

$$\Delta MFI_{tot} = \frac{\sum_{i \in SI_{cat,tp1=B}} SI_{long,i}^{comb} \cdot MFI_{i,tp2} \cdot LMV_{i,tp2}}{\sum_{i \in SI_{cat,tp1=B}} SI_{long,i}^{comb} \cdot LMV_{i,tp2}} - \frac{\sum_{i \in SI_{cat,tp1=B}} SI_{long,i}^{comb} \cdot MFI_{i,tp1} \cdot LMV_{i,tp1}}{\sum_{i \in SI_{cat,tp1=B}} SI_{long,i}^{comb} \cdot LMV_{i,tp1}}$$

Note: AMRA uses SI_{long} values combined from both timepoints to ensure only reliable results from evaluable muscles with acceptable MRI signal quality are included:

REACH TRIAL

$$SI_{long}^{comb} = SI_{long,tp1} \cdot SI_{long,tp2}$$

Absolute change in LMV_{tot} (L):

$$\Delta LMV_{tot} = \sum_{i \in SI_{cat,tp1=B}} SI_{long,i}^{comb} \cdot (LMV_{i,tp2} - LMV_{i,tp1})$$

Relative change in LMV_{tot} (%):

$$\Delta LMV_{tot}^{relative} = \sum_{i \in SI_{cat,tp1=B}} SI_{long,i}^{comb} \cdot \left(\frac{LMV_{i,tp2} - LMV_{i,tp1}}{LMV_{i,tp1}} \right)$$

Absolute change in MFF_{tot} (pp):

$$\Delta MFF_{tot} = \left(1 - \frac{\sum_{i \in SI_{cat,tp1=B}} SI_{long,i}^{comb} \cdot LMV_{i,tp2}}{\sum_{i \in SI_{cat,tp1=B}} SI_{long,i}^{comb} \cdot TMV_{i,tp2}} \right) - \left(1 - \frac{\sum_{i \in SI_{cat,tp1=B}} SI_{long,i}^{comb} \cdot LMV_{i,tp1}}{\sum_{i \in SI_{cat,tp1=B}} SI_{long,i}^{comb} \cdot TMV_{i,tp1}} \right)$$

Important note regarding AMRA terminology:

AMRA uses non-standard variable names for the longitudinal composite results. These will be mapped to standard variable names for the analysis:

AMRA Variable:	Analysis Variable:
Reference Screening (TP1) at the Screening Visit	Study-level Baseline Value (BASE at Screening)
Reference Screening (TP1) at Visit Week xx	Visit-level Baseline Value (BASE at Visit Week xx)
Week xx (TP2) at Visit Week xx	Visit-level Actual Value (AVAL at Visit Week xx)

REACH TRIAL

Change from Reference Screening at Visit Week xx	Visit-level Absolute Change (CHG at Visit Week xx)
Change from Reference Screening at Visit Week xx, (%)	Visit-level Percent Change (PCHG at Visit Week xx)

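### SAP Appendix C prints the relative change in total lean muscle volume as an unnormalised sum of per-muscle ratios, which matches neither its label nor the SAP's own definition of percentage change

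*SAP*

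**What the plan says.** Appendix C describes the composite MRI results that the vendor derives for each muscle group. Step 3 of the Week 24 procedure, which is repeated at Week 48, lists four delivered change results. One is the "relative change in LMV" total, in percent. Step 3 says the change results are obtained from the visit's TP1 and TP2 values, meaning the reference and follow-up composites of Steps 1 and 2.

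Later in the appendix the equations are printed for B muscles. In plain notation, with s_i the combined eligibility flag of muscle i:

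- absolute change in total LMV: `Σ s_i (LMV_i,2 − LMV_i,1)`, in litres;
- the line headed "Relative change in LMV" (for the total), labelled as a percentage: `Σ s_i [(LMV_i,2 − LMV_i,1) / LMV_i,1]`;
- changes in MFI and MFF: differences between two ratios, each a sum over muscles divided by a sum over muscles.

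The combined flag is the product of the longitudinal quality flags at the two timepoints. Each of these is defined "with values of 0 or 1 (where 0 = presence of major or minor signal quality issues". The closing table of Appendix C maps the percent form of the change to "Visit-level Percent Change (PCHG at Visit Week xx".

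SAP Section 9.2 defines percentage (relative) change, for all summaries, as 100 times the difference from baseline divided by baseline.

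**The concern.** A relative change in a total is the change in the total divided by the starting total. The printed expression has no common denominator, and the flags are 0 or 1, so they select muscles without normalising the sum. The result therefore grows with the number of eligible B muscles.

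That number differs between patients. It can also change between visits, because Appendix C drops a muscle when its signal quality fails and lets it return later. If the printed rule were followed, two patients with the same proportional loss would get different values, and one patient's value could move between Week 24 and Week 48 because of image quality alone.

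There is a practical risk as well. A programmer checking the vendor's variable against the printed equation would aim for a different number from one checking it against Section 9.2.

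**Working it through.** **Inputs.** The equations, flags and variable mapping are from SAP Appendix C. The definition of percentage change is from SAP Section 9.2. The ceiling of 36 muscles is from Appendix C and Section 9.3.1.5. The documents give no expected number of B muscles, so k below is an assumption between 1 and 36. The upper end would need every measured muscle to be category B.

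**Formulas compared**, all times 100 so that they are in percent:

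- (a) as printed: `100 × Σ s_i (LMV_i,2 − LMV_i,1) / LMV_i,1`, each ratio formed before summing;
- (b) Section 9.2 applied to the total: `100 × [Σ s_i (LMV_i,2 − LMV_i,1)] / [Σ s_i LMV_i,1]`;
- (c) mean of per-muscle changes: (a) divided by `Σ s_i`.

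**Uniform loss of 1%.** Each ratio is −0.01, so (a) is 100 × k × (−0.01) = −k percent. In (b) the numerator is −0.01 times the denominator, so the answer is −1% for every k.

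| Eligible muscles k (assumed) | (a) printed, ×100 | (b) change in total | (c) mean |
|---|---|---|---|
| 1 | −1% | −1% | −1% |
| 2 | −2% | −1% | −1% |
| 5 | −5% | −1% | −1% |
| 10 | −10% | −1% | −1% |
| 20 | −20% | −1% | −1% |
| 36 (ceiling) | −36% | −1% | −1% |

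Without the factor of 100, the printed line for k = 20 gives −0.20, although its label says percent.

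**Effect of eligibility alone.** Take 20 B muscles that each lose 1%. With 20, 15 or 10 of them passing the quality flag, (a) gives −20%, −15% or −10%, while (b) stays at −1%.

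**Impossible values.** With a uniform 5% loss, (a) gives 20 × (−5%) = −100% for 20 muscles and 36 × (−5%) = −180% for 36. A volume cannot fall by more than 100%.

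**Unequal changes.** Take two muscles, 1.00 L falling to 0.98 L and 0.05 L rising to 0.06 L. The reference total of 1.05 L from two muscles passes the LMV inclusion rule (at least 0.25 L from at least two muscles).

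- (b): 100 × (1.04 − 1.05)/1.05 = −0.95%.
- (a): 100 × (−0.02/1.00 + 0.01/0.05) = 100 × (−0.02 + 0.20) = +18%.
- (c): +18%/2 = +9%.

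The sign of (a) is wrong for the total. The example also shows that (b) and (c) are different quantities once muscles change unequally.

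**Consistency within a record.** The mapping table supplies BASE (visit-level reference), CHG (absolute change) and PCHG. Under Section 9.2, PCHG should equal 100 × CHG/BASE. The printed equation satisfies this only when a single muscle is eligible and the missing factor of 100 is restored.

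**The case against.** A reader might infer that the trial will report a 1% loss as −20%. The documents do not support that. Step 3 says the change values come from the composite TP1 and TP2 values, and a relative change formed from those is (TP2 − TP1)/TP1, which is the right quantity. Section 9.2 says the same. The vendor's code is not shown, so the delivered variable may already be correct and the printed line only a slip in an appendix describing someone else's calculation. This objection stands: every inflated figure above depends on literal use of the equation.

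A reader might also infer that an MRI efficacy result is at risk. It is not. The alpha-protected MRI endpoint is the absolute change in composite MFI in B muscles, and its equation is properly normalised. Section 9.3.1.5 calls the LMV composite exploratory, gives its change in litres, and lists four measures needed for the longitudinal composites; relative change is not among them. Much of the exploratory analysis section is withheld from the public text, so use of a percent change in LMV can be neither shown nor excluded.

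A misread equation was considered too. The more complex MFI and MFF fractions beside it are intact, and here the muscle index sits inside the fraction, so this does not look like a ratio of sums that lost a symbol. A lost 1/k would make it a mean of per-muscle changes, which is still not the relative change in the total. The printed page should be checked all the same.

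What remains is that the SAP contains a derivation rule that disagrees with its own label, with Section 9.2 and with Step 3.

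**Conclusion.** The printed equation is wrong for the quantity it names. If it were applied literally, and all eligible muscles changed by the same percentage, the result would be inflated by a factor equal to the eligible muscle count. It would also vary with signal quality, and it could take the wrong sign when small and large muscles move in opposite directions.

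The consequence is minor. The primary endpoint, the alpha-protected MFI endpoint and the power figures do not depend on this quantity. Randomisation should balance muscle counts on average, so the likelier harm is noisy, uninterpretable exploratory values, not bias toward one arm. The conclusion rests on the equation as it appears in the SAP. Whether the vendor's delivered variable follows it is not known.

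**What to change.** Replace the equation in Appendix C with `100 × Σ s_i (LMV_i,2 − LMV_i,1) / Σ s_i LMV_i,1`, over the same eligible muscles as the absolute change. Check the printed page of the SAP, and ask the vendor to confirm which formula produces the delivered variable.

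If the delivered variable differs, derive PCHG as 100 × CHG/BASE from the absolute change in total LMV and the visit-level Reference Screening total LMV. Both are already in the transfer. If the vendor meant a mean of per-muscle percentage changes, divide by the eligible muscle count, include the factor of 100, and rename the variable so that it is not read as a change in the total.

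The cost is one corrected equation and one check of a vendor variable. No new data are needed.
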